8.3. Lost to Follow-Up

The Investigator must make reasonable efforts to contact patients who fail to return for scheduled visits so that they will not be declared "lost to follow-up." Patients will be considered "lost to follow-up" only after reasonable, documented attempts to reach the patient prove unsuccessful. These attempts include, but are not limited to, the following:

1. Attempt contact at all telephone numbers for the patient and his/her listed contacts (to be collected in the source documents at the patient's entry into the study), as applicable.
2. Contact the patient's primary care physician, referring specialist, or other healthcare professional, as applicable.
3. Send emails and texts, and certified letters through the postal service to all the patient's addresses and contacts, as applicable.

4. Review available medical records/notes for details of hospitalizations, clinic visits, or other procedures that may indicate the status of the patient, as applicable.
5. Perform an internet search for additional contact information, as applicable.
6. Check local, regional, and national public records to locate the patient or search for mortality status as allowed by law, as applicable.

The information and dates of attempted contact must be recorded in the patient's records and the patient's final status recorded in the appropriate eCRF. Once all attempts to contact the patient have been exhausted and documented, the Sponsor or Sponsor's designee should be contacted for additional guidance.

8.4. Early Termination Visit

If possible, the ETV should take place within 14 days after withdrawal. Procedures listed on the Schedule of Assessments ([Table 1](#)) should be performed at the ETV.

8.5. Termination or Suspension of the Study

The Sponsor has the right to terminate the study at any time in case of SAEs or circumstances concerning KZR-616 or the company, that makes further treatment of patients impossible. In this event, Investigators will be informed of the reason for study termination.

9. ADVERSE EVENTS

9.1. Adverse Event Reporting

9.1.1. Definition of an Adverse Event

An AE is defined as any untoward medical occurrence in a clinical study patient administered a medicinal product, which does not necessarily have a causal relationship with this treatment. An AE can therefore be any unfavorable and unintended sign (including an abnormal laboratory finding), symptom, or disease temporally associated with the use of a medicinal (investigational) product, whether or not it is related to the medicinal (investigational) product. This includes an exacerbation of pre-existing conditions or events, intercurrent illnesses, drug interaction or the significant worsening of the indication under investigation that is not recorded elsewhere in the eCRF under specific efficacy assessments. Anticipated fluctuations of pre-existing conditions, including the disease under study, that do not represent a clinically significant exacerbation or worsening need not be considered.

It is the responsibility of the Investigator to document all AEs that occur during the study. AEs will be elicited by asking the patient a nonleading question such as, “Have you experienced any new or changed symptoms since we last asked/since your last visit?” Adverse events should be reported on the appropriate page of the eCRF.

9.1.2. Assessment of Severity

Severity of AEs will be graded according to the NCI-CTCAE (Version 4.03). If there is a change in severity of an AE, it must be recorded as a separate event.

9.1.3. Assessment of Causality

Adverse events will be deemed related to KZR-616 unless clearly unrelated to KZR-616.

The Investigator will assess the causal relationship between KZR-616 and the AE. One of the categories in [Table 3](#) should be selected based on medical judgment, considering the definitions and all contributing factors.

Table 3 **Causality Categories**

Related	A clinical event, including laboratory test abnormality, that occurs in a plausible time relationship to treatment administration, and that concurrent disease or other drugs or chemicals cannot explain. The response to withdrawal of the treatment (dechallenge ^a) should be clinically plausible. The event must be definitive pharmacologically or phenomenologically, using a satisfactory rechallenge ^b procedure, if necessary.
Unrelated	A clinical event, including laboratory test abnormality, with little or no temporal relationship to treatment administration. May have negative dechallenge ^a and rechallenge ^b information. Typically explained by extraneous factors (eg, concomitant disease, environmental factors, or other drugs or chemicals).

Abbreviations: AE=adverse event

- a Dechallenge: Upon discontinuation of a drug suspected of causing an AE, the symptoms of the AE disappear partially or completely, within a reasonable time from drug discontinuation, (positive dechallenge), or the symptoms continue despite withdrawal of the drug (negative dechallenge). Note that there are exceptions when an AE does not disappear upon discontinuation of the drug, yet drug-relatedness clearly exists (eg, bone marrow suppression, fixed drug eruptions, or tardive dyskinesia).
- b Rechallenge: Upon re-administration of a drug suspected of causing an AE in a specific patient in the past, the AE recurs upon exposure (positive rechallenge), or the AE does not recur (negative rechallenge).

9.1.4. Action Taken with Regard to KZR-616

The Investigator will describe the action taken with KZR-616 in the appropriate section of the eCRF, as follows:

- None
- KZR-616 stopped
- KZR-616 temporarily interrupted
- KZR-616 dose reduced (with written confirmation from Medical Monitor)
- Other (specify)

9.1.5. Follow-up of Adverse Events

Adverse events are intended to be collected according to the procedures outlined above from the time of informed consent and continuing for 30 days following the last dose, or the EOS Visit, whichever occurs later.

All Investigators should follow up patient AEs until the event is resolved or until, in the opinion of the Investigator, the event is stabilized or determined to be chronic. Details of AE resolution must be documented in the eCRF.

9.1.6. Documentation and Reporting of Adverse Events

Adverse events (including SAEs) should be reported and documented in accordance with the procedures outlined below. All AEs occurring during the study must be documented on the relevant eCRF pages. The following data should be documented for each AE.

- Diagnosis, or description of the symptoms if a diagnosis is not established
- Classification of 'serious' or 'not serious'
- Severity
- Date of first occurrence and date of resolution (if applicable)
- Action taken with regard to KZR-616
- Outcome of the event (unknown, recovered, not yet recovered, recovered with sequelae, death [with date and cause reported])

9.2. Serious Adverse Events

9.2.1. Definition of a Serious Adverse Event

An SAE is any untoward medical occurrence or affect that, at any dose:

- Results in death
- Is life-threatening (An AE is life-threatening if the patient was at immediate risk of death from the event as it occurred, ie, it does not include a reaction that might have caused death if it had occurred in a more serious form.)
- Requires or prolongs inpatient hospitalization. (Complications occurring during hospitalization are AEs and are considered SAEs if they cause prolongation of the current hospitalization. Hospitalization for elective treatment of a pre-existing non-worsening condition is not, however, considered an AE. The details of such hospitalizations must be recorded on the medical history or physical examination page of the eCRF.)
- Results in persistent or significant disability/incapacity. (An AE is incapacitating or disabling if it results in a substantial and/or permanent disruption of the patient's ability to carry out normal life functions.)
- Results in a congenital anomaly/birth defect.

In addition, medical and scientific judgement is required to decide if prompt notification is required in situations other than those defined for SAEs above. This may include any event that the Investigator regards as serious that did not strictly meet the criteria above but may have jeopardized the patient or required intervention to prevent one of the outcomes listed above, or

that would suggest any significant hazard, contraindication, side effect, or precaution that may be associated with the use of KZR-616.

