2.2.2. Safety Endpoints

- Incidence, nature, and severity of AEs and serious adverse events (SAEs)
- Incidence of AEs leading to KZR-616 discontinuation
- Changes in standard laboratory parameters and vital signs

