7.2.6.3. Physical Examination

Complete physical examinations will be performed at the on-site visits specified on the Schedule of Assessments ([Table 1](#)). A complete physical examination should include assessments of at least the following systems: general appearance, head, ears, eyes, nose and throat, neck, dermatological, respiratory, cardiovascular, abdomen, extremities, neurological, musculoskeletal.

At other visits (including other on-site visits and unscheduled visits), a limited physical examination may be performed as directed by the patient complaints and the clinical judgment of the Investigator. Medically significant changes from physical examination will be recorded as AEs. Muscle evaluation findings captured in the muscle assessment instruments will not be recorded unless they are classifiable as SAEs, as per [Section 9.2.1](#).

Limited physical examinations will be performed at telehealth visits.

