9.2.2. Serious Adverse Event Reporting and Documentation Requirements

An SAE must be reported (see [Section 9.1.6](#)) by the Investigator if it occurs from the time of signed consent through 30 days after the last dose of KZR-616, whether or not the SAE is considered to be related to KZR-616. After the reporting period, SAEs should be reported if the Investigator assesses the event to be related to KZR-616. An SAE report consists of the SAE form, provided separately, along with requested additional source documentation as considered necessary.

Serious adverse events that occur during the reporting period must be reported by the Investigator via entry of data into the eCRF within 24 hours from the time the Investigator becomes aware of the SAE. This entry will trigger an email notification to the Serious Adverse Event Reporting e-mail address (see [Study Personnel](#) page) that an SAE has occurred. If the electronic data capture (EDC) system is down or unavailable, a copy of the SAE form should be completed and emailed or faxed by the Investigator to the Serious Adverse Event Reporting e-mail address or dedicated fax (see [Study Personnel](#) page) within 24 hours from the time the Investigator becomes aware of the SAE. Once the EDC system is available, the SAE should be entered in the eCRF. The Investigator should not wait for additional information to fully document the SAE before reporting it, though additional information may be requested.

Requested source documentation (ie, relevant laboratory results, hospital case records, or autopsy reports) that is considered necessary should be provided separately to the Serious Adverse Event Reporting e-mail address (see [Study Personnel](#) page) using a cover sheet.

Instances of death, congenital abnormality, or an event of such clinical concern as to influence the overall assessment of safety, if brought to the attention of the Investigator at any time after cessation of KZR-616 administration and linked by the Investigator to this study, should be reported to the Study Monitor.

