9.4. New or Worsening Disease Manifestations

New or worsening manifestation(s) of PM or DM should not be recorded as AEs unless they are assessed as serious.

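### Section 9.2.1 leaves events that jeopardised the patient or needed intervention outside its SAE list, so their SAE status and 24-hour reporting can differ by site

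*Combined protocol and SAP*

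**What the plan says.** Section 9.2.1 lists five outcomes that make an event an SAE: death, immediate threat to life, new or prolonged inpatient hospitalisation, persistent or significant disability, and congenital anomaly. The paragraph after the list begins: "In addition, medical and scientific judgement is required to decide if prompt notification is required in situations other than those defined for SAEs above". Among its examples is "any event that the Investigator regards as serious that did not strictly meet the criteria above but may have jeopardized the patient". It also names events in which treatment was needed to avert a listed outcome, and events that point to a significant hazard of the drug. It sets no time limit and no reporting route.

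Several other sections rely on seriousness or on that definition:

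- Section 2.2.2 names as a safety endpoint "Incidence, nature, and severity of AEs and serious adverse events (SAEs"), and Section 10 plans the table.
- Section 9.2.2 says that SAEs in the reporting period "must be reported by the Investigator via entry of data into the eCRF within 24 hours" of the investigator becoming aware.
- Section 9.1.6 requires every AE to be documented, including "Classification of 'serious' or 'not serious".
- Section 7.2.6.3 says that muscle findings held in the muscle instruments "will not be recorded unless they are classifiable as SAEs, as per" Section 9.2.1.
- Section 9.4 says that new or worsening polymyositis or dermatomyositis "should not be recorded as AEs unless they are assessed as serious".
- Section 9.1.1 counts significant worsening of the disease under study as an AE only where the efficacy assessments do not already hold it.

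**The concern.** The protocol creates a class of events that the investigator regards as serious but that do not meet its own definition of an SAE. An event that put the patient at risk and was treated in time may meet none of the five outcomes because the treatment worked. Such events matter in an open-label extension whose purpose includes long-term safety.

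Two things are at stake. The first is timely reporting, because the 24-hour rule is written for SAEs. Expedited reporting to authorities in Sections 9.2.2 and 9.6.1 also requires a reaction to be serious. The second is the SAE count. The study has no comparator and no hypothesis test, so its safety conclusions rest on descriptive counts. Those counts are hard to interpret if up to 24 sites (Section 3.3) can answer the serious or not-serious question differently for the same event.

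**Working it through.** The plan states no SAE rate to reproduce, so the check is mainly a comparison of the sections.

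**Step 1: status under Section 9.2.1.** The five bullets form the definition. The following paragraph places its events among situations other than those defined above, and asks judgement to decide only about notification. On that wording they are not SAEs. The same paragraph says the investigator regards them as serious, and Section 9.1.6 asks for a binary answer without saying which one applies.

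**Step 2: the 24-hour report.** Section 9.2.2 applies it to SAEs. The only other 24-hour rule for adverse events is in Section 9.5.1, for the tolerability symptom complex and thrombotic microangiopathy, whatever their seriousness. An event from Step 1 that is neither of these has no stated deadline.

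**Step 3: a non-myositis event.** Section 9.1.6 still requires it to be documented as an AE, with severity. What can be lost is SAE status, and with it the SAE count and the SAE deadline.

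**Step 4: a muscle or myositis event.** Take a worsening of myositis that is scored on the muscle instruments, treated without hospitalisation, neither life-threatening nor significantly disabling, and regarded as serious by the investigator.

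| Section | Test applied | Result for this event |
|---|---|---|
| 7.2.6.3 | SAE as per Section 9.2.1 | Fails on the five bullets |
| 9.1.1 | Not already held in efficacy assessments | Fails, because it is held there |
| 9.4 | Assessed as serious | Can pass, because the investigator regards it as serious |

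Two tests keep the event out of the AE data and one can admit it. The outcome depends on which section the site follows.

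**Step 5: weight of one patient.** Section 4.1 gives a maximum of 24 patients. Incidence = patients with at least one SAE / 24, so one patient contributes 1/24 = 0.0417, or 4.2 percentage points. This applies only to a patient with no other SAE.

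For illustration only, assume one to three such patients: 1/24 = 4.2%, 2/24 = 8.3%, 3/24 = 12.5%. The exact (Clopper-Pearson) 95% interval for 0/24 is 0 to 1 − 0.025^(1/24) = 14.2%; for 2/24 it is 1.0% to 27.0%. These counts are assumed. The documents give no basis for choosing among them.

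**The case against.** The strongest reply is that the disputed paragraph sits under the heading that defines an SAE and opens as an addition to the list. Section 7.2.6.3 cites the whole of Section 9.2.1, not the bullets alone. An investigator who regards an event as serious would naturally mark it serious, and it would then be counted and reported. This is a fair reading, and it means that loss from the SAE count is not certain. It does not remove the problem, because the paragraph's own words set these events apart from those defined as SAEs. A site that follows them literally is equally compliant.

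A reader might go further and infer that muscle or myositis events of this kind are not recorded anywhere. The documents do not support that. Section 7.2.6.3 concerns findings already captured in the instruments, Section 9.4 bars recording only as AEs and excepts events assessed as serious, and Section 6.2.1.1 requires the reason for any added myositis treatment to be documented. Avoiding double recording of disease activity is also a reasonable aim. What stands is that those records carry no seriousness or causality assessment and trigger no SAE alert.

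Other safeguards exist. Section 10 tabulates adverse events by grade and summarises discontinuations and treatment changes due to AEs. Section 8.1.1 has triggers that do not depend on SAE status, including repeated events of Grade 3 or higher. These limit the consequence for patient safety, but they do not make SAE classification consistent.

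**Conclusion.** The concern holds as a defect of definition. As written, Section 9.2.1 keeps these events outside the SAE criteria, the mandatory 24-hour report (unless they are events of special interest) and SAE incidence, while its description of them as serious invites some sites to do the opposite. Muscle and myositis events face three different tests and may be absent from both the AE and the SAE tables, though not from the database.

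The scale is 4.2 percentage points of SAE incidence per affected patient, assuming the full 24 patients are enrolled and treated and that the patient has no other SAE. The total effect cannot be stated, because the number of such patients is unknown.

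Two stronger conclusions are tempting and should not be drawn. One is that SAE incidence is necessarily biased low. That would require every site to apply the literal reading, and Section 9.1.6 leaves the classification open. The other is that any event treated without hospitalisation escapes the SAE definition. It does not, because such an event can still be life-threatening or significantly disabling, and both are on the list.

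**What to change.** Add a sixth bullet to the list in Section 9.2.1: an event that, in medical judgement, jeopardised the patient or required intervention to prevent one of the listed outcomes is an SAE. The Section 9.2.2 deadline and the Section 2.2.2 incidence endpoint then apply to it without further change. Events that only suggest a hazard or precaution can stay under discretionary notification, provided the text says that they are not SAEs on that ground alone.

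Align Sections 7.2.6.3, 9.1.1 and 9.4 so that each uses the same test: a muscle or myositis event is recorded as an AE when it is an SAE under the revised Section 9.2.1. The bullet alone would leave the three tests unreconciled.

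The cost is a short amendment to the wording, a few more 24-hour reports and a possibly higher SAE count. Judgement remains part of the new criterion, so some variation between sites will persist, but every site will be applying the same rule. No treatment rule changes.

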9.2.2. Serious Adverse Event Reporting and Documentation Requirements

An SAE must be reported (see [Section 9.1.6](#)) by the Investigator if it occurs from the time of signed consent through 30 days after the last dose of KZR-616, whether or not the SAE is considered to be related to KZR-616. After the reporting period, SAEs should be reported if the Investigator assesses the event to be related to KZR-616. An SAE report consists of the SAE form, provided separately, along with requested additional source documentation as considered necessary.

Serious adverse events that occur during the reporting period must be reported by the Investigator via entry of data into the eCRF within 24 hours from the time the Investigator becomes aware of the SAE. This entry will trigger an email notification to the Serious Adverse Event Reporting e-mail address (see [Study Personnel](#) page) that an SAE has occurred. If the electronic data capture (EDC) system is down or unavailable, a copy of the SAE form should be completed and emailed or faxed by the Investigator to the Serious Adverse Event Reporting e-mail address or dedicated fax (see [Study Personnel](#) page) within 24 hours from the time the Investigator becomes aware of the SAE. Once the EDC system is available, the SAE should be entered in the eCRF. The Investigator should not wait for additional information to fully document the SAE before reporting it, though additional information may be requested.

Requested source documentation (ie, relevant laboratory results, hospital case records, or autopsy reports) that is considered necessary should be provided separately to the Serious Adverse Event Reporting e-mail address (see [Study Personnel](#) page) using a cover sheet.

Instances of death, congenital abnormality, or an event of such clinical concern as to influence the overall assessment of safety, if brought to the attention of the Investigator at any time after cessation of KZR-616 administration and linked by the Investigator to this study, should be reported to the Study Monitor.

The Sponsor and/or designee will promptly notify all relevant Investigators and the regulatory authorities of findings that could adversely affect the safety of patients, impact the conduct of the study, or alter the DMC (or appropriate alternative)/Institutional Review Board (IRB)/Independent Ethics Committee (IEC) approval/favorable opinion of the study. In addition, the Sponsor or designee will expedite the reporting of all adverse reactions that are both serious and unexpected to all concerned Investigators, to the DMC (or appropriate alternative)IRBs/IECs where required, and to relevant regulatory authorities.

For SAEs that have been reported in the KZR-616 development program, please refer to the most current KZR-616 Investigator's Brochure.

9.3. Pregnancy Reporting

Pregnancy occurring in female patients or female partners of male patients participating in the study or during a clinical investigation must be reported to the [REDACTED] (see [Study Personnel](#) page) within 24 hours and entered into the EDC. The outcome of a pregnancy should be followed up carefully, and any abnormal outcome for the mother or the child should be

reported. Infants should be followed for a minimum of 8 weeks, and all findings should be reported to the Sponsor. KZR-616 is to be discontinued immediately upon Investigator knowledge of the pregnancy and reported as per [Section 8.2](#).

If the outcome of the pregnancy meets a criterion for immediate classification as an SAE (ie, spontaneous abortion [for which any congenital anomaly detected in an aborted fetus is to be documented], stillbirth, neonatal death, or congenital anomaly), the Investigator should follow the procedures for expedited reporting of SAEs as outlined in [Section 9.2.2](#).

Full details will be recorded on the withdrawal page of the eCRF, or an SAE report will be completed if the patient has completed the study.

